To assess the durability of responses, patients who achieved 50% regrowth from baseline (a 50% reduction in baseline SALT score) during the first 6 months, will continue to be followed for an additional 6 months off treatment or until it is determined that relapse has occurred. Percent hair regrowth from baseline will be determined by SALT measurements during the observational phase at weeks 28, 32, 36, 40, 44 and 48. Relapse will be defined as any recurrence of hair loss in responders (subjects achieving greater than 50% decrease in SALT score from baseline during the first 6 months of the study) who had achieved stable regrowth without continued loss for at least 2 months; and loss of $\geq 25\%$ of regrowth in patients who had achieved 50% regrowth but still had chronic low grade hair loss.

Nonresponders to 6 months study treatment (defined as failure to achieve 50% improvement in SALT score at week 24 compared to baseline) will not be required to participate in the 6mth follow-up period but will be given the option of receiving monthly IL TAC 2.5mg/ml, 5mg/ml or 10mg/ml injections for 6 months if deemed appropriate by the investigator. The dosage to be utilized (2.5mg/ml vs. 5mg/ml vs. 10mg/ml) will be based on clinical considerations, unless study data is available to support preference of one dose versus the

other. Patients identified by unblinded study personnel as having previously been treated with active drug or with obvious signs of atrophy or other indications suggesting they have already been treated with active drug for 6 months will not be given the option of continuing IL TAC as it is unlikely that they will respond if they have not responded by 6 months unless available evidence suggests that utilization of a different dosage is more likely to be efficacious and safe.

Human Subjects Involvement, Characteristics, and Design

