Screening: A complete medical history will be taken. Patients will be specifically asked about renal, hepatic or adrenal abnormalities and pregnancy (women of child bearing potential only). In keeping with current standard of care, no routine blood work will be done, unless it is deemed necessary by the investigator. Patients will be randomly assigned to IL TAC 2.5mg/ml, IL TAC 5mg/ml or IL TAC 10mg/ml or intralesional saline in a 1:1:1:1 ratio based on a computer generated randomization list. The list will be generated prior to study initiation. Based on the randomization list, patients will be assigned to treatment vs. placebo based on the order in which they are enrolled. The assignment will be made by study personnel not involved in making clinical assessments or evaluations. The patient and the assessing physicians will remain blinded to the treatment assignment for the duration of the study. Baseline assessments of disease severity will be done, including SALT, Physician global assessment (PGA), patient global assessment and patient quality of life assessment. Patients will have study medication injected once per month by the study physician in accordance with current standard of care clinical practice. Per current clinical practice, attempts will be made to treat all areas of hair loss due to AA, however (also in accordance with current standard of care in clinical practice) the dose of intralesional triamcinolone injected will be limited to a maximum of 30mg per month(16, 4). Therefore, patients being

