treated with IL TAC 2.5mg/ml will have up to a maximum of 12ml of drug injected, those treated with IL TAC 5mg/ml will have up to a maximum of 6ml of drug injected, while patients being treated with IL TAC 10mg/ml will receive a maximum of up to 3ml of drug injected. In an attempt to maintain the blinding of the evaluating investigator, patients receiving saline placebo, will have either 3ml, 6ml, or 12ml drawn up at the discretion of the unblinded study staff member preparing the medication. When possible, an unblinded physician investigator will perform study medication injections. If the blinded evaluating investigator must perform injections, the syringes will be covered such that the solution contained within is not visible. The entire syringe will be covered. After injections are completed, the unblended study team member will collect the used and unused syringes and calculate the total volume injected. This amount will be recorded and concealed to maintain integrity.

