Baseline to Week 48: Patients will receive intradermal injection of study medication once per month to all, or as many as possible, areas of hair loss up to the maximum dose of 30mg IL TAC per month, for a total of 6 months. Injections will be performed at baseline, weeks 4, 8, 12, 16 and 20. Injection areas will be chosen based on the investigator's clinical assessment of factors including but not limited to, areas of most active shedding, areas of maximum medical and cosmetic benefit, avoidance of any areas of pre-existing atrophy, etc. Patients will be seen at weeks 28, 32, 36, 40, 44 and 48 after end of treatment in order to assess the frequency and timing of relapse. Nonresponders to 6 months study treatment (defined as failure to achieve 50% improvement in SALT score at week 24 compared to baseline) will not be required to participate in the 6 month follow-up period but will be given the option of receiving monthly IL TAC 2.5mg/ml, 5mg/ml or 10mg/ml injections for 6 months if deemed appropriate by the investigator. The dosage to be utilized (2.5mg/ml vs. 5mg/ml vs. 10mg/ml) will be based on clinical considerations, unless study data is available to support preference of one dose versus the other. Patients identified by unblinded study personnel as having received TAC or with obvious signs of atrophy or other indications suggesting they have already been treated with active drug for 6 months will not be given the option of continuing IL TAC as it is unlikely that they will respond if they have not responded by 6 months unless available evidence suggests that utilization of a different dosage is more likely to be efficacious and safe.

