Efficacy evaluations: SALT, PGA, and Patient global assessment will be performed at every visit. PGA and patient evaluations will be based on similar 100mm visual analog scales. Patient quality of life assessments, performed at baseline, weeks 12, 24, 36, and 48, will be based on changes in the Dermatology Life Quality Index DLQI – adapted for hair loss, or the Dermatology Quality of Life Scales. Blood draws for safety assessments and immunology will be drawn at weeks 4, 12, 24 and 28(if needed for safety labs). Scalp biopsies for immunologic parameters will be obtained at baseline, and at one time point between weeks 4 and 20. Additional biopsies and blood draws may be obtained as clinically indicated. Since the timeline to regrowth may vary from subject to subject, unscheduled biopsies and blood draws will insure that tissue and blood samples are obtained at optimal timepoints to evaluate the changes occurring at the onset of growth or in the event of any unexpected clinical change. In addition, areas that are resistant to treatment may be biopsied to determine the cellular and immunologic differences of those areas compared to areas that are responding to treatment.

The patient will be given the option to agree to, or decline, the additional biopsies and blood draws.

Standardized photographs of the subject's scalp will be taken at Baseline, Week 4, 8, 12, 16, 20, 24, 36 and 48 and will be used to support determination of percent hair regrowth. Photography will consist of a high resolution digital camera mounted on a stereotactic arm. Patients will be positioned using a fixed guide after which photographs of the entire scalp will be taken at standardized locations and at a fixed distance. At a minimum, photographs of the crown, right and left lateral scalp and posterior scalp (views consistent with those used in the SALT measurement) will be taken.

Visit Schedule and Assessments

Screening assessments and all scheduled study visits are outlined in the Table of Study Assessments (please see below).

Informed consent

Written informed consent will be obtained from all patients for this study by the principal investigator or his/her designee prior to any protocol-specific procedures. The study will be conducted in accordance with the Food and Drug Administration (FDA) approved revision of the Declaration of Helsinki, current FDA regulations, and International Conference on Harmonization (ICH) guidelines.

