Week 24 +/- 7 days – End of treatment also end of study for nonresponders not continuing on to open label treatment and beginning of open label treatment for nonresponders continuing to open label treatment

- Vital signs, body weight
- Physical and dermatological examination
- Adverse events reporting, concomitant medication review
- Photography
- Physician evaluation utilizing the PGA and SALT scale
- Patient global assessment and quality of life assessment
- Urine pregnancy testing
- Clinical laboratory evaluation
- Optional scalp biopsy (4mm punch biopsy) and blood collection for immunological studies
- IL TAC injection for qualified nonresponders continuing to open label treatment

Weeks 28, 32, 36, 40, 44 and 48 +/- 7 days– Observational Period for responders or IL TAC Injection period for nonresponders deemed appropriate for open label injection

- Vital signs, body weight

- Physical and dermatological examination (only week 48)
- Adverse events reporting, concomitant medication review
- Photography (weeks 36 and 48)
- Physician evaluation utilizing the PGA and SALT scale
- Patient global assessment
- Patient quality of life assessment (only weeks 36 and 48)
- Optional Scalp biopsy (4mm punch biopsy) at additional timepoints at the discretion of the principal investigator and with the consent of the subject, based upon perceived utility in context of individual patient response to therapy and durability of that response.
- Optional Blood collection for immunological studies at additional timepoints at the discretion of the principal investigator and with the consent of the subject.
- IL TAC injection for qualified nonresponders.

Early Termination

- Vital signs, body weight
- Physical and dermatological examination
- Adverse events reporting, concomitant medication review
- Photography
- Physician evaluation utilizing the PGA and SALT scale
- Patient global assessment and quality of life assessment
- Clinical laboratory evaluation
- Scalp biopsy (4mm punch biopsy) – if indicated and if patient agreeable to biopsy and 2 week f/u for suture removal if deemed necessary.
- Blood collection for immunological studies

Unscheduled Visits

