A 3-month interim analysis of the primary and secondary outcomes will be performed by an independent group in order to determine if statistical significance has been attained. A Haybittle-Peto rule for alpha spending (Haybittle 1971; Peto et al. 1976) will be followed for the interim analysis. If statistical evidence of efficacy is attained at 3 months and if the safety profile is acceptable, all patients will be offered the option of receiving open label active drug for the remaining duration of the trial.

To compare the frequency of occurrence of relapse in responders (followed for 6 months off therapy) across the four groups, we will employ a chi-squared test for comparing multiple proportions.

Furthermore, to compare the timing of relapse in responders (followed for 6 months off therapy) across the four groups, we will use tools from survival analysis (or, time-to-event analysis, with relapse as the event of interest). More specifically, first, we will conduct a descriptive analysis by graphically comparing the Kaplan-Meier survival (time-to-relapse) curves for the four groups. Next, we will use the log-rank test to formally test the null hypothesis of no difference between the survival functions of the four groups.

Specific Aim 2. To identify a clinical correlation between treatment outcome and down modulation of key AA-associated immunohistopathological markers and biomarkers in the treated skin; including NKG2DL expression in the hair follicle, immune infiltration (CD8⁺NKG2D⁺ cells) and expression of interferon response genes.

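### The study-long blinding claim does not hold for nonresponders after week 24, because the open-label offer depends on true allocation (minor correction)

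*Combined protocol and SAP*

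**What the plan says.** The blinding statement is in Study procedures, Screening: "The patient and the assessing physicians will remain blinded to the treatment assignment for the duration of the study". It carries no qualification, and scheduled ratings run to week 48.

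The open-label rule appears in Specific Aim 1 and again under Baseline to Week 48. Week-24 nonresponders may be offered six months of open-label IL TAC if the investigator judges it appropriate. The option is withheld from two groups:

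- "Patients identified by unblinded study personnel as having previously been treated with active drug" (Specific Aim 1; the Baseline to Week 48 text is equivalent);
- those "or with obvious signs of atrophy or other indications suggesting they have already been treated with active drug for 6 months".

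The only stated exception is "unless available evidence suggests that utilization of a different dosage is more likely to be efficacious and safe".

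The Week 24 visit is described as the "beginning of open label treatment for nonresponders continuing to open label treatment". Its list contains SALT and PGA (one item), patient global and quality of life (the next item) and, last, the open-label injection. No text requires any rating to be signed before the decision is given.

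**The concern.** A decision driven by true allocation is shown to the patient and the investigator. A reader of the protocol knows that an offer is, by default, not made to someone known to have had active drug. An offer is therefore evidence of saline, and the whole-study blind stops being true for nonresponders once the decision is released.

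The interim option in the Data Analysis Plan differs. There "all patients will be offered the option of receiving open label active drug for the remaining duration of the trial", so that offer says nothing about the arm.

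Two sets of secondary ratings could be affected: any week-24 rating completed after the decision is known, and the weeks 28-48 ratings of nonresponders on open-label drug. The latter enter the week-36 and week-48 group comparisons listed under Secondary efficacy outcomes, which the Data Analysis Plan analyses by intention to treat. Relapse outcomes concern responders only and are untouched.

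**Working it through.** **Inputs.** From Sample size: 17 patients per arm, 68 in total; response 10% on saline and 50% on each active dose. From the randomization text: 1:1:1:1, so 17 saline and 51 active. The plan gives no figure for what an offer reveals. Its sample size does reproduce: for a 3-df chi-squared test at 5% and 80% power the noncentrality is 10.90, and 10.90/0.4² = 68.1, against 68 stated.

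**Nonresponders at week 24.**
- Saline: 17 × 0.90 = 15.3
- Active: 51 × 0.50 = 25.5
- Total: 40.8 of 68 (60%)
- Saline among nonresponders, before any decision: 15.3/40.8 = 37.5%

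**After an offer.** Let s be the share of saline nonresponders offered drug and e the share of active nonresponders offered drug (different-dose exception, or allocation not checked). Then

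P(saline | offer) = 15.3s / (15.3s + 25.5e).

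The documents give neither s nor e, so the values below are assumptions.

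| s | e | Calculation | P(saline given offer) |
|---|---|---|---|
| 1 | 0 | 15.3/15.3 | 100% |
| 1 | 0.10 | 15.3/17.85 | 85.7% |
| 1 | 0.25 | 15.3/21.675 | 70.6% |
| 1 | 0.50 | 15.3/28.05 | 54.5% |
| 0.75 | 0.50 | 11.475/24.225 | 47.4% |
| 1 | 0.75 | 15.3/34.425 | 44.4% |
| any s = e | | 15.3/40.8 | 37.5% |

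Only the ratio of s to e matters. An offer carries no information when s = e, and it points to saline whenever s exceeds e, which is what the default refusal is written to produce.

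**Sensitivity to the saline rate.** The section on clinical experience with IL TAC mentions 20% spontaneous recovery in an earlier study. With that rate there are 17 × 0.80 = 13.6 saline nonresponders. The starting figure becomes 13.6/39.1 = 34.8%, and with s = 1 an offer gives 100%, 68.1% and 51.6% at e = 0, 0.25 and 0.50. The picture does not change.

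**Order of steps at week 24.** Nonresponse is defined by the week-24 SALT, so that score must exist before an offer is possible. PGA is in the same list item as SALT. Patient global and quality of life are a separate item, and nothing in the text fixes when they are completed relative to the decision.

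**The case against.** The case on the other side is strong about consequences.

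- **Primary endpoint.** A reader might infer that the week-24 response rate is biased. The documents do not support this. SALT must be scored before an offer, photographs "will be used to support determination of percent hair regrowth", and case report forms are checked against source. Only later revision of a recorded score would remain, and no text suggests it. This stands.
- **Week-24 layout.** The visit list puts ratings first and the injection last. That suggests the intended order and, in practice, largely protects PGA. It is not a sign-off rule, so it does not settle the patient-completed ratings.
- **Patients' knowledge.** Patient ratings can be influenced only if patients know the refusal rule. The available text does not show that they do. This stands.
- **Size of the signal.** It is tempting to read an offer as near proof of saline, or to treat 55% as a floor. Neither follows. The 55% needs every saline nonresponder to be offered drug and only half of the active ones. Other assumptions give 47%, 44% or no rise. Three doses leave room for the exception, and no text requires an allocation check for every nonresponder.
- **Starting point.** An assessor who has seen atrophy already has some information, so 37.5% is not necessarily that assessor's starting point and not all of the rise is due to the offer.
- **Weeks 28-48.** Treatment in this period is openly labelled, and the group comparisons are already affected by crossover. Refused nonresponders leave at week 24, so they have no scheduled later ratings.
- **Existing separation.** "When possible, an unblinded physician investigator will perform study medication injections", and withholding more steroid from patients who did not respond to it is a reasoned clinical choice.

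What survives is that open-label labelling discloses current treatment, whereas the protocol claims continued blinding to the original assignment. Nothing elsewhere in the documents reconciles that claim with the refusal rule.

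**Conclusion.** The point holds as a minor, low-severity correction. The protocol claims a blind for the whole study that its open-label rule does not deliver for nonresponders, who at the planning rates are about 41 of 68 patients. The signal ranges from certainty of saline to none, depending on offer rates that the documents do not give. It exceeds the 37.5% starting figure whenever saline nonresponders are offered drug more often than active ones.

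The exposed items are mainly week-24 patient global and quality of life, conditional on patients knowing the rule, and the weeks 28-48 ratings of open-label nonresponders. A reader might infer that the leak favours active drug. The direction is not established: favourable ratings of former saline patients on open-label drug would narrow the arm difference.

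**What to change.** 1. In the Week 24 visit list, require SALT, PGA, patient global and quality of life to be completed and signed before unblinded staff release the open-label decision.
2. Amend the blinding sentence under Study procedures, Screening, so that for nonresponders the blind is claimed only up to that release.
3. Report weeks 28-48 ratings of open-label nonresponders as unblinded.

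The cost is protocol wording, a slightly longer week-24 visit and a less favourable blinding statement. The change protects the week-24 ratings and corrects the claim. It does not restore a blind in weeks 28-48 or deal with crossover.

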in which fewer than 10% are expected to achieve this magnitude of hair regrowth spontaneously. In contrast, clinical experience would suggest that approximately 50% of subjects treated with either dose of IL TAC may achieve $\geq 50\%$ improvement in SALT score after 6 months of treatment. The goal of this study is to validate or refute this clinical impression and to objectively and precisely quantify the treatment effect of 2.5mg/ml, 5mg/ml or 10mg/ml of IL TAC in AA.

Subjects will be randomized 1:1:1:1 to the placebo or treatment arms, and will receive 6 months of treatment with the study medication or placebo. IL TAC 2.5mg/ml, 5mg/ml, 10mg/ml or placebo will be administered at baseline, then every 4 weeks thereafter for 5 cycles (weeks 4, 8, 12, 16, 20) for a total treatment period of 6 months. Percent hair regrowth from baseline will be determined by SALT measurements following 4, 8, 12, 20 and 24 weeks of treatment. Punch biopsies and peripheral blood will be obtained at baseline prior to treatment, and then once again at a time point between weeks 4 and 20, to be determined by the investigator as indicated by clinical considerations such as variation in the timeline to regrowth from one subject to another, for immunomonitoring/biomarker studies. Additional, optional scalp biopsies and blood draws may be taken at other key time points in order to monitor response to therapy at the discretion of the investigator and with the consent of the study subject. Efficacy will be measured by change in hair re-growth as determined by physical exam and photography, as well as by patient and physician global evaluation scores. Physician and patient global evaluation scores will be determined based on the use of similar 100mm Visual Analogue scales with 0 labeled as no scalp hair loss and 100 labeled as complete scalp hair loss. Patients and physicians will place a vertical mark along the horizontal line depending on their assessment of the degree of hair loss present at the time of assessment.

As secondary endpoints, efficacy will be measured by changes in hair re-growth as a continuous variable as determined by physical exam, SALT score and Canfield photography, as well as patient and physician global evaluation scores.

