The use of human subjects is proposed in this application. Informed consent will be obtained from each subject prior to any study related procedures. After informed consent has been obtained, potential subjects will be screened to ensure they meet diagnostic and safety criteria for inclusion in the study. Subjects will then be randomly assigned via a randomization list to one of three doses (2.5mg/ml versus 5mg/ml versus 10mg/ml) of IL TAC or placebo (intralesional saline) in a 1:1:1:1 ratio. Bacteriostatic saline is chosen as a diluent and placebo instead of xylocaine as the injection stings less. The concentration, frequency of injection of the study medication and diluents used are determined based on current standard of care in clinical practice for the treatment of patients with alopecia areata. Therefore, patients being treated with IL TAC 2.5mg/ml will have up to a maximum of 12ml of drug injected, those treated with IL TAC 5mg/ml will have up to a maximum of 6ml of drug injected, while patients being treated with IL TAC 10mg/ml will receive a maximum of up to 3ml of drug injected. In an attempt to maintain the blinding of the evaluating investigator, patients receiving saline placebo, will have either 3ml, 6ml, or 12ml drawn up drawn up as appropriate for the extent of hair loss present and at the discretion of the unblinded study staff member preparing the medication. The entire syringe will be covered. After injections are completed, the unblinded study team member will collect the used and unused syringes and calculate the total volume injected. This amount will be recorded and concealed to maintain integrity. During the course of the study, subjects will be closely monitored for efficacy and the occurrence of adverse events. Determination of immunologic outcome measures will require the collection of blood samples (peripheral blood draws) as well as skin biopsies from the scalp. The subject population will consist of 68 patients with a diagnosis of patchy AA of recent onset (duration of at least 3 months) who have consented to participation in the trial and have met all inclusion and exclusion criteria. Patients will be 18 to 75 years old, and be deemed to be in good general health. We do not intend to enroll patients from vulnerable populations.

Inclusion criteria

- Patients 18 to 75 years of age
- Patients with a diagnosis of patch type alopecia areata

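### Unblinded staff choose the saline volume while active volume is capped by arm, so volume read against extent of hair loss gives a partial clue to active versus placebo; a randomised placebo ceiling would remove that clue

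*Combined protocol and SAP*

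**What the plan says.** The document is the combined protocol and SAP.

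- **Placebo volume, Study procedures (Screening paragraph):** saline patients "will have either 3ml, 6ml, or 12ml drawn up at the discretion of the unblinded study staff member preparing the medication".
- **Placebo volume, Human Subjects Involvement, Characteristics, and Design:** the same three volumes, "drawn up as appropriate for the extent of hair loss present and at the discretion of the unblinded study staff member". Extent is a criterion here and is absent from Study procedures.
- **Active volume, both sections:** at the lowest strength, patients "treated with IL TAC 2.5mg/ml will have up to a maximum of 12ml of drug injected". The corresponding limit at 5 mg/ml is 6 ml, and at the highest strength they "will receive a maximum of up to 3ml of drug injected". Study procedures says that injections aim at all areas of loss, within 30 mg per month.
- **Allocation, Methods:** "Subjects will be randomized 1:1:1:1 to the placebo or treatment arms".
- **Blinding safeguards, Study procedures:** patient and assessing physicians are to stay blinded throughout. An unblinded physician injects where feasible, the whole syringe is covered, and unblinded staff work out the injected total and keep it hidden. The fallback is: "If the blinded evaluating investigator must perform injections, the syringes will be covered such that the solution contained within is not visible".

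**The concern.** The variable saline volumes are there to protect the blind, so the plan already treats volume as a threat. But the choice is left to someone who knows the allocation, under two different rules, and it need not respect the ceilings that bind the active arms. A patient with extensive loss who receives only a small volume is then more likely to be on a concentrated active dose than on saline.

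Covering the syringe hides the solution. It does not hide the number of injections from the person giving or receiving them. At about 0.1 ml per site, which the protocol's review of clinical experience gives as general practice, 3, 6 and 12 ml are about 30, 60 and 120 sites.

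The outcomes leave room for expectation. SALT rests on estimated areas, the physician and patient global scores are marks on a visual analogue scale, and photographs only support the regrowth rating. With 17 patients per arm, one changed responder call moves an arm's response rate by 1/17 = 5.9 percentage points.

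**Working it through.** **The plan's own figures.** The ceilings agree with the 30 mg monthly cap: 12 × 2.5 = 6 × 5 = 3 × 10 = 30 mg. The plan gives no figure for how well volume is masked, so that is derived here.

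**Inputs.** Allocation 1:1:1:1, so P(placebo) = 25% before any volume is seen. Ceilings are 3, 6 and 12 ml for 10, 5 and 2.5 mg/ml. Let V be the volume that the patient's extent calls for. An active patient then receives the smaller of V and the arm's ceiling.

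**Step 1: placebo follows extent exactly (strongest case).** Each arm holds a quarter of patients. An arm whose ceiling is below V falls visibly short and is known to be active.

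| Volume needed | Arms that fall short | Identifiable as active | P(placebo) among the rest |
|---|---|---|---|
| V ≤ 3 ml | none | 0% | 1/4 = 25% |
| 3 < V ≤ 6 ml | 10 mg/ml | 25% | 1/3 = 33% |
| V > 6 ml | 10 and 5 mg/ml | 50% | 1/2 = 50% |

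**Step 2: looser discretion.** The documents give no probabilities for the staff's choice, so two splits are assumed, for patients in whom every ceiling binds. With q the share of placebo patients given a volume, P(placebo | volume) = 0.25q / (0.25q + 0.25).

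- Shares 80/15/5% (12, 6, 3 ml): 0.20/0.45 = 44%; 0.0375/0.2875 = 13%; 0.0125/0.2625 = 5%.
- Shares 60/30/10%: 0.15/0.40 = 37.5%; 0.075/0.325 = 23%; 0.025/0.275 = 9%.

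The clue weakens but stays away from 25%.

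**Step 3: placebo ceiling randomised 1:1:1.** Each code holds 1/12 of all patients.

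- V ≤ 3 ml: all arms receive V, so 25%.
- 3 < V ≤ 6 ml: at 3 ml, (1/12)/(1/12 + 1/4) = 25%; at V, (2/12)/(2/12 + 2/4) = 25%.
- V > 6 ml: (1/12)/(1/12 + 1/4) = 25% at each of the three volumes.

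Seventeen placebo patients can be split only 6/6/5. For V > 6 ml this gives 6/(6 + 17) = 26.1% and 5/(5 + 17) = 22.7%. The middle band stays inside that range: for example, 11/(11 + 34) = 24.4% at V when the 3 ml code has six patients.

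**Step 4: what volume still says about dose.** When all ceilings bind, after the change P(10 mg/ml | 3 ml) = (1/4)/(1/4 + 1/12) = 75%, and likewise for 5 mg/ml at 6 ml and 2.5 mg/ml at 12 ml. A best guess of the exact arm is right 75% of the time, against 25% without the clue. Under the rule in Step 1 it is also right 0.25 + 0.25 + 0.25 = 75% of the time. The change does not touch this.

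**The case against.** The strongest reply is that active volume is a ceiling and also follows extent. A reader might take the volumes as fixed by arm and infer that half of all subjects could be recognised as active. The documents do not support that. It would need every patient to require more than 6 ml, yet entry allows up to 50% loss with no stated minimum and the Data Analysis Plan anticipates a 0-25% stratum. For small patches the four arms can look the same. This stands, and it is why the size is given by band.

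Second, by default the evaluator who scores SALT, the primary measure, does not inject, and the volume record is hidden. This reduces the leak but does not close it, because the plan lets the evaluator inject when needed.

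Third, a patient experiences one volume, has no other for comparison, and is not said to know the volume rule; the patient global score is only secondary. This also stands: the patient route works only if patients learn that volume differs by arm.

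The objection does not reach the disagreement between the two sections, or the fact that a perceptible feature of the control arm is set by someone who knows the allocation.

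**Conclusion.** The concern holds in a limited form. Volume read against extent is informative about active versus placebo, from no clue (3 ml or less needed) to half of patients identifiable as active (more than 6 ml needed). Those figures assume that placebo follows extent exactly and that the observer can judge both the volume given and the volume needed. How many trial patients fall in each band cannot be worked out from the documents.

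A reader might infer that volume reveals allocation. It does not: even in the strongest case P(placebo) never exceeds 50%, so no placebo patient is identified. A reader might also infer that randomising the volume restores full blinding at no cost. It removes only the active-versus-placebo clue. The dose clue (75% when ceilings bind) remains, so the head-to-head dose comparison in the Data Analysis Plan stays exposed. No bias in the response rates has been quantified; the documents give no basis for that.

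**What to change.** Reconcile the Human Subjects section with Study procedures, and replace staff discretion in both with one rule, for example:

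> The randomisation list assigns each placebo patient a volume code of 3, 6 or 12 ml, in a ratio of about 1:1:1 (6/6/5 for 17 patients). The code is kept for all visits and is the maximum saline volume; within it, injections follow the area treated exactly as in the active arms.

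The code must be a ceiling. If it were a volume to be delivered in full, a placebo patient with a small patch and a 12 ml code would be recognisable as placebo, because active patients are injected only as their areas require. It should stay constant because a change between the six injection visits could itself be a clue; the plan does not say whether volume is constant now.

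The cost is one extra code in the list and edits to two passages. The 68 patients, the alpha and the visits do not change. Some placebo patients would have less area injected than staff would have chosen, which the sponsor should weigh.

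The plan should also state that volume still points to dose, as a limitation of the dose comparison. Keeping the evaluator from ever injecting, and asking patients and evaluators to guess the allocation, would limit and measure what remains. The staffing cost of the former cannot be judged from the documents.
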